2.3.3 Changes & Additions on Trial Medication

Sections 8.6, 8.7 and 8.8 of the protocol describe the different possible changes and additions on trial medication:

- 1. Add-on non-study treatments for participants with high BP,
- 2. Down-titration or temporary cessation of trial medication,
- 3. Temporary change from investigational medicinal product (IMP) to open label therapy arising from

pandemic-related IMP supply shortages,

4. Early discontinuation of the trial medication.

Add-on non-study treatments, down-titration and temporary cessation as described in the protocol will aim to retain participants on trial medication while addressing symptoms and/or out of range blood pressure levels. For early discontinuation of trial medication, the participant will be followed-up until the end of the trial unless the participant withdraws consent. In all these scenarios, there is no need to unblind the participants – the specific scenarios for unblinding are referred to in the protocol Section 11.4.

2.4 Outcomes

2.4.1 Efficacy Outcomes

2.4.1.1 Primary

Difference in change in home seated mean SBP from randomization to follow-up Week 12.

2.4.1.2 Secondary

- Difference in change in clinic seated mean SBP from randomization to follow-up Week 12.
- Difference in change in clinic seated mean SBP from randomization to follow-up Week 6.
- Difference in change in clinic seated mean DBP from randomization to follow-up Week 12.
- Difference in change in clinic seated mean DBP from randomization to follow-up Week 6.
- Percentage of participants with clinic seated mean SBP <140 and DBP <90 mmHg at follow-up Week 12.
- Percentage of participants with clinic seated mean SBP <140 and DBP <90 mmHg at follow-up Week 6.
- Percentage of participants with clinic seated mean SBP <130 and DBP <80 mmHg at follow-up Week 12.
- Percentage of participants with clinic seated mean SBP <130 and DBP <80 mmHg at follow-up Week 6.
- Difference in change in home seated mean SBP from randomization to follow-up Week 6.
- Difference in change in home seated mean DBP from randomization to follow-up Week 12.
- Difference in change in home seated mean DBP from randomization to follow-up Week 6.
- Difference in change in trough home seated mean SBP from randomization to follow-up Week 12.
- Difference in change in trough home seated mean SBP from randomization to follow-up Week 6.
- Percentage of participants with home seated mean SBP <135 and DBP <85 mmHg at follow-up Week 12.
- Percentage of participants with home seated mean SBP <135 and DBP <85 mmHg at follow-up Week 6.
- Percentage of participants with home seated mean SBP <130 and DBP <80 mmHg at follow-up Week 12.
- Percentage of participants with home seated mean SBP <130 and DBP <80 mmHg at follow-up Week 6.

2.4.2 Safety Outcomes

2.4.2.1 Primary

Percentage of participants discontinued trial medication due to an Adverse Event (AE) or a Serious Adverse Event (SAE) from randomization to follow-up Week 12.

2.4.2.2 Secondary

- Percentage of participants discontinued trial medication due to AE/SAE from randomization to follow-up Week 6.
- Percentage of participants with an SAE from randomization to follow-up Week 12.
- Percentage of participants with an SAE from randomization to follow-up Week 6.

- Percentage of participants with symptomatic hypotension from randomization to follow-up Week 12.
- Percentage of participants with symptomatic hypotension from randomization to follow-up Week 6.
- Percentage of participants with serum sodium concentration below 135 mmol/l at follow-up Week 12.
- Percentage of participants with serum sodium concentration below 135 mmol/l at follow-up Week 6.
- Percentage of participants with serum sodium concentration above 145 mmol/l at follow-up Week 12.
- Percentage of participants with serum sodium concentration above 145 mmol/l at follow-up Week 6.
- Percentage of participants with serum potassium concentration below 3.5 mmol/l at follow-up Week 12.
- Percentage of participants with serum potassium concentration below 3.5 mmol/l at follow-up Week 6.
- Percentage of participants with serum potassium concentration above 5.5 mmol/l at follow-up Week 12.
- Percentage of participants with serum potassium concentration above 5.5 mmol/l at follow-up Week 6.
- Percentage of participants with serum sodium <135mmol/l or >145 mmol/l, and/or serum potassium <3.5 mmol/l or >5.5mmol/l at follow-up Week 12.
- Percentage of participants with serum sodium <135mmol/l or >145 mmol/l, and/or serum potassium <3.5 mmol/l or >5.5mmol/l at follow-up Week 6.
- Percentage of participants with eGFR drop of over 30% from randomization to follow-up Week 12.
- Percentage of participants with eGFR drop of over 30% from randomization to follow-up Week 6.
- Percentage of participants with orthostatic hypotension at Week 6,
- Percentage of participants with orthostatic hypotension at Week 12
- Percentage of participants with orthostatic hypertension at Week 6,
- Percentage of participants with orthostatic hypertension at Week 12

In addition, descriptive safety data will be reported on:

- Percentage of participants discontinued trial medication due to AE/SAE during the active run-in period.
- All SAEs, by severity and by System Organ Class (SOC) criteria in the run-in period and by trial medication group in the randomized period and safety follow-up period.

2.6 Changes in the Conduct of the Study or Planned Analyses

2.6.1 Changes in the Conduct of the Study

Recruitment to the study was terminated before randomizing 1500 participants. Details are provided in Appendix 2.

2.6.2 Changes in Planned Analysis

Multiple analysis sections have been expanded within this document from the protocol-specified analyses. Clarifications and expansions include:

- The addition of an estimands section
- Detailed descriptions of mixed models for repeated measures and multiple imputations
- Clarified calculation methods for derivation of primary endpoint
- Use of multiple populations for analysis, including the use of supportive and sensitivity analysis
- Expansion of analysis methods to be used for secondary efficacy and secondary safety endpoint analysis

3 STATISTICAL ANALYSIS

3.1 Interim Analyses

The DSMB met periodically throughout the duration of the trial for data review. No analyses on unblinded efficacy results were performed. Observed standard deviation of the home BP measurements on the overall sample informed updated power calculations periodically through the study: see Appendix 2.

3.2 Multi-Center Trials

Analysis of demographic and baseline characteristics, efficacy and safety data will be pooled across all sites.

For the primary analysis, mixed models with repeated measures (MMRM) will be applied accounting for correlation between observations within site.

3.3 Multiplicity Adjustment

All tests are to be two-sided with a nominal level of α set at 5%. Since the purpose of the trial is to demonstrate effects on all three of the designated primary efficacy endpoint comparisons simultaneously (i.e. GMRx2 has to be statistically significantly superior at two-sided p<0.05 to each of the possible dual combinations for the trial to be regarded as positive), there is no need for adjustment of the Type I error for the primary endpoint, according to ICH E9 Guidance and FDA Guidance 'Multiple Endpoints in Clinical Trials. Guidance for Industry, 2017'. The impact on Type II error and sample size has been carefully considered, in that the estimated power for each separate comparison is >97% and so the power for all three comparisons is >91% (i.e., 0.97³ = 0.91).

The secondary efficacy parameters measure different aspects of the same underlying treatment effect evaluated in the primary efficacy endpoint, that is the effect of GMRx2 compared to dual combinations on blood pressure, and do not demonstrate additional new treatment effects of the drug, but rather clarify the effect already demonstrated by the primary analysis. No type I error adjustment is proposed to account for multiplicity for secondary efficacy endpoint analyses.

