12.3. Sample Size & Power Calculation

A sample size of 1500 participants (600 in GMRx2 and 300 in each of the dual combination groups) provides 97% power to detect a minimum difference of 3 mmHg in home seated mean SBP for each of the three comparisons of GMRx2 vs dual therapy, assuming a common standard deviation of 11 mmHg within each group. The overall power for all three comparisons will therefore be over 90%. Randomizing 1500 may necessitate at least 2000 participants entering the run-in treatment. A systematic review of previous trials of triple vs dual combination therapy demonstrated, on average, a 5.4/3.2 mmHg greater reduction in clinic BP with triple therapy,⁶¹ and it is anticipated that the current trial will have similar rates of drop-in and drop-out as observed in those trials. A systematic review comparing BP reductions from different BP measurement methods indicated that on average reductions in home BP were about 20% less than those seen for clinic BP.⁶² In three recent trials that utilized home BP measurement protocols very similar to those planned for this trial, the average SD of change in home SBP was 11 mmHg.^{21,63,64}

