Appendix 2: Additional Power Calculations

As noted in Section 2.5, the initial power calculation presented is a very conservative calculation, which is based on a simple comparison of mean values and a common standard deviation of the actual SBP values i.e., T-test of sample means with equal variances. Our modelling approach – a multivariable mixed model – is similar to an ANCOVA (Analysis of Covariance) type of analysis which will explicitly consider an adjustment for the baseline SBP values. A sample size calculation based on the ANCOVA (which would be more powerful than the simple and more conservative t-test approach used above) and on the same assumption as before (allocation ratio of 2:1 of GMRx2 vs dual, alpha 0.05, equal SD across arms of 11) would lead to the following power: 98% if regressing the SBP values to the specific covariate set the R² (proportion of variance explained) achieved is 10%, 99% if R² is 20%, 99.6% if R² is 30% with overall power respectively 95%, 97% and 99%. These R² values were considered to be conservative, since two similar, completed BP trials (TRIUMPH and QUARTET) each had R² values over 40% in mixed models on SBP data using treatment, time, their interaction and SBP at baseline and compared with the null model.

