Supply chain and logistics issues, substantial recruitment delays related to the COVID-19 pandemic and other unanticipated issues caused unplanned and significant trial conduct interruptions. As a result of these delays, a re-supply of IMP became infeasible. In addition, there had been independent review of study power at two Steering Committee meetings (6 Dec 2022 and 14 Feb 2023), based on the prespecified statistical approach of a mixed model repeated measures and blinded standard deviation of the overall sample, that the trial likely would have more statistical power than the univariate approach on which initial powering was modelled, as detailed above. These estimates were made without any reference to unblinded data. The Sponsor informed the Steering Committee of the pending IMP supply situation at their meeting on 11 April 2023, and given these challenges and blinded study power assessment that indicated the trial already had as much power as originally planned, the Steering Committees, the Steering Committee Chair wrote to the Sponsor on 21 April 2023 recommending a premature termination of recruitment. Based on the foregoing, the Company decided to terminate recruitment to the study. The final number of patients randomized was over 90% of the planned sample size.

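### Must the power figures in SAP 3.3 be restated because recruitment stopped short of 1500?

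*SAP*

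**What the plan says.** Protocol 12.3 and SAP 2.5 set out the planning calculation: 1500 randomized (600 to GMRx2, 300 to each dual arm), a 3 mmHg difference in home SBP, SD 11 mmHg and 97% power per comparison. SAP 2.5 adds the two-sided 5% level. Protocol 12.3 puts overall power above 90%.

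SAP 3.3 requires all three comparisons to be significant and states that "the estimated power for each separate comparison is >97% and so the power for all three comparisons is >91" per cent, obtained by cubing 0.97.

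SAP 2.6.1 then reports: "Recruitment to the study was terminated before randomizing 1500 participants". SAP Appendix 2 gives the final size only as a fraction: "The final number of patients randomized was over 90% of the planned sample size". It explains the stop by the failure of trial-drug re-supply together with a "blinded study power assessment that indicated the trial already had as much power as originally planned". It also gives ANCOVA-based power of 98%, 99% and 99.6% per comparison for R² of 10%, 20% and 30%, "with overall power respectively 95%, 97% and 99" per cent.

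On the blinded SD, SAP 3.1 says "Observed standard deviation of the home BP measurements on the overall sample informed updated power calculations periodically through the study" and refers to Appendix 2.

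On the meaning of the 11 mmHg, Protocol 12.3 reports that in three earlier trials "the average SD of change in home SBP was 11 mmHg". Appendix 2 says the initial calculation used "a common standard deviation of the actual SBP values".

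**The concern.** SAP version 2.0 is dated 17 November 2023, about seven months after the Steering Committee Chair recommended ending recruitment (21 April 2023). A present-tense power statement with no N, in a document that elsewhere says the target was missed, reads as a claim about the trial as it was run. By the unadjusted method behind it, the claim would not hold over most of the range that Appendix 2 allows.

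Because all three comparisons must succeed, joint power is what matters, and it falls faster than power per comparison. Power was also one of the stated grounds for stopping, yet the cross-reference in SAP 3.1 leads to no observed SD, no N and no updated power value. Finally, the benefit of baseline adjustment depends on whether 11 mmHg is the SD of change or of the values themselves, and the two documents differ. If the true power were well below plan, a missed comparison could be hard to interpret.

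**Working it through.** **Inputs.** Difference 3 mmHg, SD 11 mmHg, two-sided 5%, 2:1 within each comparison (Protocol 12.3; SAP 2.3.2, 2.5, 3.3). The final N is not stated; N = 1350 (the bound implied by over 90%) and N = 1425 are assumptions. Everyone randomized is taken to contribute.

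**Formula.** Power = Φ(3 / SE − 1.96), with SE = 11·√(1−R²)·√(1/n₁ + 1/n₂), n₁ = 0.4N and n₂ = 0.2N. Joint power is the cube, as in SAP 3.3. A trivariate normal with correlation (1/600)/(1/600 + 1/300) = 1/3 allows for the shared GMRx2 arm.

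**Reproducing SAP 3.3 at 1500.** SE = 11·√(1/600 + 1/300) = 0.778; 3/0.778 = 3.857; Φ(1.897) = 97.1%. The cube is 91.6% (0.97³ = 91.3%), or 92.3% with the shared arm. The stated figures are correct.

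**Reproducing Appendix 2 at 1500.** R² of 10%, 20% and 30% gives 98.2%, 99.1% and 99.6% each, and 94.8%, 97.2% and 98.8% by cubing. These match too.

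**Unadjusted power at smaller N.**

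| N | Each | All three (cube) | All three (shared arm) |
|---|---|---|---|
| 1500 | 97.1% | 91.6% | 92.3% |
| 1425 | 96.4% | 89.6% | 90.5% |
| 1350 | 95.5% | 87.2% | 88.4% |

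At 1350: SE = 11·√(1/540 + 1/270) = 0.820; 3/0.820 = 3.659; Φ(1.699) = 95.5%. On this basis 97% needs about 1,488 randomized, and the cube drops below 90% under about 1,440.

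**Power under the planned model.** Protocol 12.4 and SAP 3.10.2.2 put baseline home SBP in the primary model. Power depends on N/(1−R²), so the 1500 figures return when R² = 1 − N/1500. That is 10% at 1350 (residual SD 11·√0.9 = 10.4) and 5% at 1425 (11·√0.95 = 10.7). At 1350:

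| R² | Each | All three (cube) |
|---|---|---|
| 10% | 97.1% | 91.6% |
| 20% | 98.3% | 95.1% |
| 30% | 99.2% | 97.6% |
| 40% | 99.7% | 99.1% |

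**Does the meaning of the SD change this?** Assume equal variances at baseline and Week 12, with correlation ρ.

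- If 11 is the SD of change, the adjusted SD is 11·√((1+ρ)/2), so the variance reduction is (1−ρ)/2. This is at least 10% when ρ ≤ 0.80.
- If 11 is the SD of actual values, the adjusted SD is 11·√(1−ρ²), so the reduction is ρ². This is at least 10% when ρ ≥ √0.10 = 0.32.

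At 1350 and ρ = 0.5 both readings give SD 9.53 and 98.8% per comparison. At ρ = 0.8 the change reading gives SD 10.44 and 97.1%; the actual-value reading gives SD 6.60 and over 99.9%. For any ρ from 0.32 to 0.80, planned power is kept on either reading.

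**The case for a change.** The strongest case for a change is that the power argument for stopping cannot be checked from these documents. SAP 3.1 promises the SD-based updates in Appendix 2, and Appendix 2 reports only their conclusion. The R² above 40% is not a clean substitute: it comes from models of SBP that also contained treatment, time and their interaction, so part of it is not baseline gain, and it is not an R² for change. At a correlation of 0.9 on the change scale, the adjusted SD is 11·√0.95 = 10.7 and power at 1350 is 96.4% each and 89.5% jointly, slightly under plan. A sentence in SAP 2.5 is also garbled: it runs the success rule into the overall power.

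All of this stands as description. It does not show that any stated figure is wrong. SAP 2.5 supplies the N that SAP 3.3 omits, and SAP 3.3 speaks of type II error and sample size as matters already considered, which is planning language. Appendix 2 calls its starting point the initial calculation and carries its assumptions forward. The shortfall is disclosed, with the dates and blinded basis of both power reviews. Even the unfavourable 0.9 case misses the planned joint power of 91.6% by about two percentage points.

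**Conclusion.** No change to the plan is needed. The >97% and >91% are correct planning values for 1500, and SAP 2.5 identifies them as such. The unadjusted loss is at most 1.6 percentage points per comparison (97.1% to 95.5%) and 4.4 jointly (91.6% to 87.2%), and only at the assumed floor of 1350 with no gain from baseline adjustment. The prespecified model makes that adjustment, and a 10% variance reduction removes the loss. With equal variances, either reading of the 11 mmHg provides this for baseline-to-Week-12 correlations from 0.32 to 0.80; the true correlation is not in the documents.

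The remaining points are clerical or matters of reporting: no planning label in SAP 3.3, no numbers behind the cross-reference in SAP 3.1, two descriptions of one SD, and a merged sentence in SAP 2.5. Recruitment had ended before this SAP version, so recomputed power could not affect the conduct of the trial. The number randomized is already a planned disposition output (SAP 3.6), and the confidence intervals will show the precision achieved. Analysts following the SAP as written reach the same estimates and the same decision on all three comparisons.

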3.4 Populations for Analysis

3.4.1 Screened Set

The Screened Set includes all participants who have provided consent and have a screening number, regardless of whether they have been randomized or treated with study treatment.

3.4.2 Safety Set

The Safety Set is defined as all participants who took at least one dose of study treatment, including during Period 1 single-blind run-in. For the analysis of the safety endpoints, participants will be analyzed in the treatment group they actually received.

3.4.3 Efficacy Populations

For all efficacy analyses, participants will be analyzed in the treatment group to which they have been randomized.

The Randomized Set will be the set of reference for reporting primary and secondary endpoints to preserve the intention-to-treat (ITT) principle. The Full Analysis Set (FAS) and other strategies proposed will be used to evaluate the robustness of the results.

3.4.3.1 Randomized Set

The Randomized Set includes all participants who have been randomized. Participants will be analyzed in the treatment group to which they have been randomized.

3.4.3.2 Full Analysis Set

The FAS is defined as all participants in the randomized set who have taken at least one dose of randomly assigned treatment. If the Randomized Set and the FAS are very similar (\leq 5% difference) in size, the efficacy analysis will not be rerun on the FAS set as a sensitivity analysis.

3.4.3.3 Per Protocol Set

The Per Protocol Set is defined as all randomized participants who did not experience an intercurrent event or major protocol deviation. Intercurrent events are defined within the Estimand Statements (Section 3.10.1). Protocol deviations are defined within Section 3.9.3. As receipt of an incorrect study treatment (wrong study treatment kid dispensed) is a major protocol deviation, participants will be grouped according to the treatment received.

3.5 General Methods

All data listings that contain an evaluation date will contain a relative study day. Two relative study days will be defined: Period 1 Relative Day (P1 Rel Day) and Post-Randomization Relative Day (PR Rel Day). For Period 1 Relative Day, pre-treatment and on-treatment study days are numbered relative to the day of the first dose of single-blind study treatment which is designated as P1 Day 1. The preceding day is P1 Day -1, the day before that is P1 Day -2, etc. Post-Randomization Relative Day will be numbered relative to the day of the first dose of the randomized medication which is designated as PR Day 1.

The planned treatment group for all participants in Period 1 is GMRx2. In Period 2, the planned treatment group is randomly assigned to be:

- 1. Triple TAI (GMRx2) : telmisartan (T) 20 mg/amlodipine (A) 2.5 mg/indapamide (I) 1.25 mg.
- 2. Dual TA: telmisartan 20 mg/amlodipine 2.5 mg.
- 3. Dual TI: telmisartan 20 mg/indapamide 1.25 mg.
- 4. Dual AI: amlodipine 2.5 mg/indapamide 1.25 mg.

Up-titration is planned to occur prior to Period 3, resulting in planned treatment at increased dose levels; however, the up-titration may not occur for reasons as specified in the protocol (Section 8.4.2). Therefore, treatments in period 3 include:

Treatment Group	Period 2: Treatment	Period 3: With Up-	Period 3: No Up-Titration
	(Planned)	titration (Planned)	
Triple – TAI	telmisartan (T) 20 mg/	telmisartan 40 mg/	same as in Period 2
	amlodipine (A) 2.5 mg/	amlodipine 5 mg/	
	indapamide (I) 1.25 mg.	indapamide 2.5 mg	
	(GMRx2 Dose2)	(GMRx2 Dose3)	
Dual – TA	telmisartan 20 mg/	telmisartan 40 mg/	same as in Period 2
	amlodipine 2.5 mg	amlodipine 5 mg	
Dual – TI	telmisartan 20 mg/	telmisartan 40 mg/	same as in Period 2
	indapamide 1.25 mg	indapamide 2.5 mg	
Dual – Al	amlodipine 2.5 mg/	amlodipine 5 mg/	same as in Period 2
	indapamide 1.25 mg	indapamide 2.5 mg	

Table 3-1 Planned Treatment Assignments Period 2 and Period 3

All output will be incorporated into Microsoft Word or Adobe Acrobat PDF files, sorted and labelled according to the ICH recommendations, and formatted to the appropriate page size(s).

Tables will be produced for appropriate demographic, baseline, efficacy, and safety parameters. For categorical variables, summary tables of the number and percentage of participants within each category (with a category for missing data) of the parameter will be presented. For continuous variables, the number of participants, mean, median, standard deviation (SD), minimum, and maximum values will be presented. Summarizations will be presented by treatment group and overall. For efficacy and safety summaries, Period 1 (active run-in period) will be summarized separately from the randomized treatment period and follow-up.

3.5.1 Computing Environment

All descriptive statistical analyses will be performed using SAS statistical software using version 9.4 or higher, unless otherwise noted. Medical history and adverse events will be coded using the Medical Dictionary for Regulatory Activities (MedDRA) Version 24.0 (or higher, as up-versioning may occur). Concomitant medications will be coded using the World Health Organization (WHO) Drug Dictionary March 2021 version (or later, as up-versioning may occur).

